We propose a randomized, double blinded, single-center trial in 80 patients with obesity to study the Effect of an anti-Obesity Medication Phentermine-Topiramate Extended Release vs placebo among patients using a wearable activity trackers in weight loss and obesity related comorbidities in 12 months. All the participants will receive a wearable activity tracker and digital wellness devices (Bluetooth scale, Bluetooth pulse oximeter and Bluetooth blood pressure monitor) as part of an intense lifestyle intervention (8 in person visits total with dietitians, physicians and other study team members. At least one contact per month virtually with a member of the study team when an in person visit is not scheduled. Subjects will be randomized 1:1 to placebo or Phentermine-topiramate ER (Dosing of 3.75/23 mg daily for 15 days, increased to 7.5/46 mg daily). Participants will be randomized according to a computer generated randomization schedule generated by the study statistician's office and submitted to the Mayo Clinic CTSA research pharmacy. Allocation will be concealed. Study end-points: a) Primary: Total body weight loss at 3 months among the groups; and b) secondary: Total body weight loss at 6, 9 and 12 months among the groups; number of steps (average per week at 3, 6, 9 and 12 months among the groups); calories tracked: number times recorded, calories per day (average per week at 3, 6, 9 and 12 months among the groups), number of exercise sessions (average per week at 3, 6, 9 and 12 months among the groups); hours/week using app/tracker (average per week at 3, 6, 9 and 12 months among the groups); weight loss difference in clinic vs. Bluetooth scale (weight loss difference 3, 6, 9 and 12 months); Quality of life SF36 (at 3, 6, 9 and 12 months among the groups); improvement in obesity-related comorbidities (diabetes/HbA1c, hypertension/SBP-DBP, hyperlipidemia/TC-LDL-HDL-Tg, Sleep apnea/CPAP, Joint Disease/pain).

Study flowsheet:

Visit schedule:

1. Visit 1-Screening visit
2. Visit 2-Baseline anthropometric and metabolic studies
3. Visit 3-Counseling / Randomization / wearable tracker, digital wellness devices and Medication assignment and disbursement.
4. Remote visit-2-week follow up (Remote visit)
5. Visit 4-4-week follow up
6. Remote visit-2 month
7. Visit 5-3 month follow up / samples collection / body composition
8. Remote visit-4 month
9. Remote visit- 5 month
10. Visit 6- 6 month follow up
11. Remote visit-7 month
12. Remote visit-8 month

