13. Visit 7-9 monthfollow up
14. Remote visit-10 month
15. Remote visit-11 month
16. Visit 8-12 month End of study

				Months												
				1		2	3	4	5	6	7	8	9	10	11	12
Study Procedures	Visit 1 Screening	Visit 2 Baseline Studies	Visit 3 Counseling and Randomization	Remote Study Visit 2-Week (+/- 3 days)	Visit 4 4-Week (+/- 3 days)	Remote Study Visits	Visit 5	Remote Study Visits	Remote Study Visits	Visit 6	Remote Study Visits	Remote Study Visits	Visit 7	Remote Study Visits	Remote Study Visits	Visit 8
Informed Consent	X															
Medical History and Physical Examination	X															
Pregnancy Test	X*	X*	X*		X*		X*			X*			X*			X*
Vital Signs	X	X	X	X	X		X			X			X			X
Metabolic Studies		X														X****
Blood Collection		X					X**			X**			X**			X**
Medication Diary																
Dispense medication			X			X			X		X		X			
Medication Reconciliation			X			X			X		X		X			

Wearable Tracker and Digital Wellness Devices Given			X													
Randomization and Medication/Placebo Prescription			X													
Behavioral Questionnaires	X***	X ^a														X
Stool Sample		X														
Adverse Event Assessment				X	X	X	X	X	X	X	X	X	X	X	X	X
Review VitalCare Measurements /pregnancy test results				X	X	X	X	X	X	X	X	X	X	X	X	X
Lifestyle Intervention Review			X													
Home Urine Pregnancy Tests Given					X		X			X			X			

* may be done up to 48 hours prior to visit.

**fasting blood draw only (basic metabolic panel, lipid panel, HbA1C, hsCRP, plasma hormones and proteomics.

***HADS, AUDIT-C and Eating disorders questionnaire only

**** Body composition, fasting blood for basic metabolic panel, lipid panel, HbA1C, hsCRP, metabolomics, plasma hormones and proteinomics

^a All questionnaires except HADS, AUDIT-C and Eating disorders questionnaire

^b Visit window for visits 5, 6, 7, 8 and all remote visit is +/- 5 days.

Randomization and Allocation

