- e) Subject must have an Apple iPhone 6s or later with iOS 13 or later and be willing to download the VitalCare (VitalTech Affiliates LLC) application from the Apple App Store.
- f) Able to provide written informed consent prior to any study procedures, and be willing and able to comply with study procedures

Exclusion criteria

- a) History of Abdominal bariatric surgery
- b) Weight is greater than 450 lbs (204 kg)
- c) Recent use (within the last three months) of any antiobesity medication
- d) Recent weight change (gain or loss weight greater than 3% TBW in the last 3 months)
- e) Positive history of chronic gastrointestinal diseases, or systemic disease that could affect gastrointestinal motility, or use of medications that may alter gastrointestinal motility, appetite or absorption, e.g., orlistat, within the last 6 months.

- f) Significant untreated psychiatric dysfunction based upon screening with the Hospital Anxiety and Depression Inventory (HAD), and the Questionnaire on Eating and Weight Patterns (binge eating disorders and bulimia). If such a dysfunction is identified by an anxiety or depression score >11 or difficulties with substance or eating disorders, the participant will be excluded and given a referral letter to his/her primary care doctor for further appraisal and follow-up.
- g) Hypersensitivity or contraindication to the study medication.
- h) Participant unable or unwilling to follow protocol including use of the wearable activity tracker, digital wellness devices, VitalCare application, or unwilling to sign consent.
- i) Principal Investigator discretion

Anthropometrics and Metabolic Characteristics studies

Anthropometrics Measurements: will be taken of height, weight, blood pressure, pulse, waist and hip ratio, respiration rate and temperature at screening, baseline, randomization day and visit 5, 6, 7, 8 and 9.

Baseline Characteristic studies:

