Urine pregnancy testing will be done at visits 1, 2, 3, 4, 5, 6, and 8 for women of child bearing potential (WOCBP). Subjects who are WOCBP will be given urine pregnancy test kits (QuickVue+ hCG Combo Test (Quidel Corporation) or similar) along with instructions to complete at home. Subjects will be instructed to complete these home pregnancy test kits and report the results during the remote study visits with the study team. If a subject has a positive urine pregnancy test result at any time the subject will be withdrawn from the study and instructed to stop use of the study medication/placebo immediately. The subject will be given a referral to their primary care provider.

Statistical Considerations

Primary endpoint: Total body weight loss at 3 months

Secondary endpoints:

- Total body weight loss at 6, 9 and 12 months
- number of steps (average per week at 3, 6, 9 and 12 months)
- calories tracked: number times recorded, calories per day (average per week at 3, 6, 9 and 12 months)
- number of exercise sessions (average per week at 3, 6, 9 and 12 months)

- hours/week using app/tracker (average per week at 3, 6, 9 and 12 months)
- weight loss difference in clinic vs. Bluetooth scale (weight loss difference 3, 6, 9 and 12 months)
- Quality of life SF36 (at 3, 6, 9 and 12 months)
- improvement in obesity-related comorbidities (diabetes/HbA1c, hypertension/SBP-DBP, hyperlipidemia/TC-LDL-HDL-Tg, Sleep apnea/CPAP, Joint Disease/pain)

Design: We propose a randomized, double-blinded, placebo-controlled trial of 80 participants with obesity to compare effects of Phentermine-topiramate ER vs placebo in weight loss with 1 year follow up.

Sample size assessment and power calculation: In our recent pilot study [with Liraglutide 3.0 mg vs. placebo], the standard deviation (SD) for the overall weight change (pre-post at 12 weeks) observed was 2.8kg [32] and observed weight loss in the control/placebo group was 6.1kg.

Conservatively assuming a standard deviation of 3kg within groups,

Difference to Detect (kg) – reflects greater weight loss in active arm vs placebo	Sample Size per group	TOTAL Sample Size	With 10% dropout at 3 months	With 15% dropout at 3 months	With 20% dropout at 3 months
1kg (ex: 7.1 vs 6.1)	143	286	318	338	358
1.5kg	64	128	142	152	160
2 kg	37	74	82	88	94

Actual power is anticipated to be higher when accounting for baseline weight using Analysis of Covariance (ANCOVA) methods.

Statistical Analysis:

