The primary analysis will be conducted under intention to treat (ITT) principles. Since study drug is administered double-blind, all subjects taking at least one dose of study drug will be included in analyses.

Primary endpoint: The primary endpoint is weight at 3 months (12 week visit), compared between groups using Analysis of Covariance (ANCOVA), adjusted for baseline weight. Subjects without follow up (dropouts) will have values imputed using multiple imputation. This approach assumes the distribution of missing data is random after conditioning on observed data in the imputation process. A secondary approach will consider complete case data, though this does not generally adhere to ITT principles.

Weight is recorded longitudinally at several post-baseline timepoints. A secondary analysis will model these longitudinal data using linear mixed effects models, adjusted for baseline weight. Additional adjustment variables will be included based on *a priori* determination by investigators that such variables may be associated with the dropout process. Thus, any dropout is assumed Missing At Random as a function of observed data. Time after randomization will be included as a discrete ordinal variable corresponding to the visit number. The primary comparison is a time by treatment group interaction, so that contrasts of the variables in the model will allow estimation of the treatment effect at each visit.

An interim analysis will be performed after 50% of subjects have completed their 3 month visit. This will allow the study team to review data quality and check assumptions related to the power calculation (including the standard deviation

above). Investigators will remain blinded to group comparisons and while investigators have no intention of stopping the study early (regardless of interim results), the analysis at study completion will be conservatively adjusted using the O'Brien-Fleming boundary (two-sided significance level of 0.0492).

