Secondary endpoints will be assessed similarly. Steps, calories, and hours using the app tracker will be collected by the device. These will be aggregated to a weekly total or daily average over the week-long period to smooth out day-to-day variation. Analyses will be performed using linear mixed effects models with these weekly total data, separately for each endpoint. Weight loss as recorded by the Bluetooth scale at home will be analyzed similarly, taking the average of assessments over the course of each week as the outcome [recall, the primary endpoint is weight loss measured in clinic at study visits]. Number of exercise sessions will be evaluated, also as a weekly total number of sessions, using generalized linear mixed effects models with the outcome analyzed as a Poisson count. The distribution of each outcome will be assessed and alternative approaches considered as necessary. Quality of Life questionnaires will be assessed at study visits and analyzed using linear mixed effects models to compare between groups. The primary outcome has been pre-specified and no adjustment will be made for comparisons of these secondary outcomes.

An exploratory aim will evaluate adherent vs non-adherent patients – and further the interaction between adherent (vs non-adherent) and randomized group, to assess whether there is a differential response to Phentermine-Topiramate among exercise adherent patients. Adherence will be defined by 80% use during the first 3 months.

Anticipated results and significance:

Our study will demonstrate the importance of combining a consumer-based wearable activity tracker with an Anti-obesity Pharmacotherapy in Obesity.

Potential pitfalls, precautions taken, and alternative strategies:

- a. Feasibility - Given high volume of patients interested in weight loss, we are confident we will recruit sufficient participants for these studies that involve only noninvasive tests and standard of care treatment.
- b. Statistical power has been addressed with appropriate sample sizes to demonstrate a difference in weight change vs. placebo.

References

- 1 Gadde, K. M. *et al.* Effects of low-dose, controlled-release, phentermine plus topiramate combination on weight and associated comorbidities in overweight and obese adults (CONQUER): a randomised, placebo-controlled, phase 3 trial. *Lancet* **377**, 1341-1352, doi:10.1016/s0140-6736(11)60205-5 (2011).

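### The clinic-versus-Bluetooth weight-loss difference is a listed secondary endpoint, but the plan neither estimates it nor assures the home readings it needs

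*Combined protocol and SAP*

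**What the plan says.** The abstract, Methods/Study Design and Statistical Considerations all list the secondary endpoint: "weight loss difference in clinic vs. Bluetooth scale (weight loss difference 3, 6, 9 and 12 months".

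Statistical Analysis opens its secondary-endpoint paragraph with "Secondary endpoints will be assessed similarly". Its one sentence on the home scale is "Weight loss as recorded by the Bluetooth scale at home will be analyzed similarly, taking the average of assessments over the course of each week". The longitudinal method for weight that this refers back to reads: "A secondary analysis will model these longitudinal data using linear mixed effects models, adjusted for baseline weight".

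On when weights exist:
- Clinic anthropometrics, including weight, are taken with "respiration rate and temperature at screening, baseline, randomization day and visit 5, 6, 7, 8 and 9" (the visit schedule itself ends at Visit 8).
- The scale is first available at "Visit 3-Counseling / Randomization / wearable tracker, digital wellness devices and Medication assignment and disbursement".
- Virtual Care sets no times at which the devices must be used. Use is encouraged but left to the participant, and the team looks at the results only at study visits.
- The procedures table has a row "Review VitalCare Measurements /pregnancy test results", marked from the 2-week remote visit onward.
- Exclusion criterion (h) removes people unable or unwilling to use the digital wellness devices.

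**The concern.** A difference in weight loss between two scales is a within-person quantity. It needs a baseline on each scale, a follow-up value on each scale close in time, and a rule for pairing them. The plan supplies none of these for the home scale. It models one home series between randomized groups, with time coded by visit number for clinic weight and by week for home weight, and gives no mapping between the two.

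The home baseline is also unnamed. It could be the first home weighing or a clinic weight, and the two choices give different answers from the same data. Wording added later can settle the definition, but it cannot recover a home weighing that was never taken around Visit 3 or around a later clinic visit. At stake is whether the trial can report this endpoint at all, and whether a reported difference reflects the scales or the choice of baseline.

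**Working it through.** **The plan's own figures.** No precision or agreement target is stated for this endpoint. The sample-size table is for the primary endpoint. Its 143, 64 and 37 per group reproduce with a two-sample t-test (SD 3 kg from the plan; two-sided 0.05 and 80% power assumed), but they have no bearing here.

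**Definition.** Let c(t) be clinic weight and suppose the home scale reads c(t) + d, with constant offset d. The endpoint is D(t) = clinic loss minus home loss. If both baselines are taken at the same time, d cancels and D(t) = 0, as it should when the scales agree on change.

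**Baseline is the first home weighing, w weeks after Visit 3.** Home loss = c(w) − c(t), so D(t) = c(0) − c(w). This is the weight lost before the first home weighing, and it is carried unchanged in kg to all four times.
- Input: 6.1 kg over 12 weeks, from the control arm of the liraglutide pilot in the sample-size section. A constant rate is assumed: 6.1 / 12 = 0.508 kg per week.
- 1 week late: 0.51 kg (1/12 = 8% of the 12-week loss). 2 weeks late: 1.02 kg (2/12 = 17%).
- First-week mean as baseline, centred at 3.5 days: 0.508 × 0.5 = 0.25 kg (4%).
- If loss is front-loaded (exponential, half of the 12-week loss by week 4, assumed): 0.91 kg at 1 week and 1.71 kg at 2 weeks (15% and 28%).

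**Baseline is a clinic weight.** Home loss = c(0) − [c(t) + d] = clinic loss − d, so D(t) = d at every time. An assumed offset of 0.5 to 1.5 kg gives a false difference of 0.5 to 1.5 kg even when both scales record the same change.

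**Effect on the arm contrast.** With an equal delay in both arms and linear loss, the home-scale arm difference at 12 weeks shrinks by w/12. For the 2 kg difference in the sample-size table, that is 2 × 1/12 = 0.17 kg or 2 × 2/12 = 0.33 kg. If both arms follow the front-loaded shape, the shrinkage is 15% or 28%. An equal offset cancels completely.

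**Achievable precision.** With an assumed SD of the paired difference of 1.0 to 1.5 kg, 64 pairs (80 less 20%) give a 95% CI half-width of 0.25 to 0.37 kg, and 40 pairs give 0.32 to 0.48 kg. Limits of agreement would be about ±2.0 to ±2.9 kg. An average artefact of 0.5 to 1.0 kg would therefore exceed the half-width in each of these cases.

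**The case against.** The strongest reply is that the readings will probably exist. Use is encouraged, the team reviews the measurements at every visit from week 2, and exclusion (h) screens out people unwilling to use the devices. That stands: a reader might infer that pairs will be missing, and the documents do not support so strong a claim. None of these provisions sets a weighing time, however, and the first review comes after treatment has started.

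A second reply is that one analysis-plan sentence would do: take the first-week mean as the home baseline, at a cost of about 0.25 kg, match the visit-week mean, and count the missing pairs. That would settle the definition and is a reasonable fallback, but it does not make the readings happen.

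Third, the natural reading of baseline weight for the clinic series is the Visit 2 baseline visit. That is fair. The gap is that no source is named for the home series. Fourth, the sizes are mostly assumptions. That is also fair: only the 6.1 kg comes from the documents, and it comes from a pilot of a different drug. The algebra does not depend on it.

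Other stronger readings also fail. Bluetooth weight is not without an analysis, since home weight loss by itself has a stated model. The treatment comparison on the primary endpoint is not affected, because it uses clinic weight. Nor do the documents show that weekly step totals will create a false arm difference. That would need unworn days counted as zero and unequal wear in a blinded trial, neither of which is stated, and hours of tracker use by group is already a planned endpoint.

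**Conclusion.** The point holds for this one secondary endpoint. Followed exactly, the plan neither estimates the listed clinic-versus-home difference nor assures the readings needed for it. The artefact is about 0.5 or 1.0 kg for a first weighing 1 or 2 weeks late, given 6.1 kg over 12 weeks at a constant rate. If a clinic weight is the baseline, the artefact equals the scale offset. These are illustrations, since actual delays and offsets are unknown. The change is worth making because it is cheap and has to be made before the readings are due, not because any main conclusion is threatened.

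**What to change.** **Protocol (Virtual Care and visit schedule).** Prompt one weighing at home on the issued scale within about a day of Visit 3, and one at home within 3 days of the actual date of each of Visits 5, 6, 7 and 8. The first should be at home, not in clinic, so that floor, clothing and time of day are closer to those of the later readings.

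**Statistical Analysis, for this endpoint only.**
- Home baseline: the first prompted home weighing.
- Clinic baseline: the randomization-day weight, leaving the primary ANCOVA covariate unchanged.
- Follow-up home value: the prompted reading, with the weekly mean as a sensitivity analysis.
- Report at each time the mean paired clinic-minus-home difference in weight loss with 95% CI, limits of agreement and number of pairs.
- Participants without a home baseline contribute only to same-visit agreement in weight.

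**Cost.** A small protocol amendment and five prompts on a scale already supplied. Prompting may slightly raise self-weighing, in both blinded arms alike. A 3-day gap leaves a timing mismatch of up to 3/7 × 0.508 = 0.22 kg, and a one-day baseline delay about 0.508 / 7 = 0.07 kg, at the same constant rate.

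**Optional.** If the tracker export holds daily wear, mean steps per worn day could be added as a sensitivity analysis. It is not needed for this point.

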0.39; $P<.001$), and energy expenditure (SMD 0.28; 95% CI 0.03 to 0.54; $P=.03$) and a nonsignificant decrease in sedentary behavior (SMD -0.20; 95% CI -0.43 to 0.03; $P=.08$) following the intervention versus control comparator across all studies in the meta-analyses. In general, included studies were at low risk of bias, except for performance bias. Heterogeneity varied across the included meta-analyses ranging from low ($I^2=3\%$) for daily step count through to high ($I^2=67\%$) for sedentary behavior. Utilizing a consumer-based wearable activity tracker as either the primary component of an intervention or as part of a broader physical activity intervention has the potential to increase physical activity participation. As the effects of physical activity interventions are often short term, the inclusion of a consumer-based wearable activity tracker may provide an effective tool to assist health professionals to provide ongoing monitoring and support²⁸.

Online support system: VitalCare (VitalTech Affiliates LLC) is a digital health platform that allows remote collection of data from the wearable tracker and digital wellness devices used as part of this study. It also will allow subjects to document study medication compliance and will allow the remote visits to be conducted through a video conference between subjects and appropriate study team members.

FDA-approved medications, devices and surgeries have shown long-term improvements in obesity and diabetes, however, their use (population penetrance) remains low (less than 1% market use). On the contrary, and despite of contradicting published literature, numerous wearable technologies specific to physical activity and diet are widely adopted with minimal long-term data or benefits. Little is known about the effect anti-obesity pharmacotherapy among patients undergoing lifestyle intervention that includes a consumer-based wearable activity tracker.

[figure not shown]
Hypothesis and Aims:

We hypothesize that anti-obesity pharmacotherapy (vs placebo) will have an effect on weight loss among patients using an activity tracker as part of a lifestyle intervention. Thus, we aimed to study in a randomized, double-blinded, placebo-control, 1-year, single-center trial the effect of Phentermine-topiramate ER (Anti-obesity Pharmacotherapy) vs placebo among patients with obesity using a wearable activity tracker as part of standard lifestyle intervention.

Methods/Study Design:

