A computer generated randomization schedule generated by the study statistician's office will be submitted to the Mayo Clinic CCaTS Research Pharmacy. Randomization will be based on guiding pharmacotherapy or placebo. Allocations will be concealed. This study will be blinded until data are transmitted to the statistician for data lock. All subjects will be given a verbal explanation of the study, provided time to read and study the written consent form and its information, given opportunities to ask questions and a copy of the consent form. Participants will be informed of their right to withdraw from the study at any time without prejudice to their clinical management now or in the future. Consent will be sought by one of the medical doctor investigators or the study coordinator, and consent will be documented by the participant's signature on the consent form. Mayo's Institutional Review Board will approve the process and protocol. All the members of multidisciplinary team for weight management (i.e. physicians, coordinators, clinical assistants, registered dietitians will remain blinded).

If unblinding is needed for subject safety the Principal Investigator or a Co-Investigator will contact a research Pharmacist or the research pharmacy manager and provide documentation of reason for study unblinding and the subject will be withdrawn from the study. The study team will document and report the reason for unblinding as required by the Mayo Clinic IRB.

Selection Participants

We plan to study a cohort of 80 patients with obesity ($BMI > 30 \text{ kg/m}^2$). Participants will be recruited from the Mayo Clinic Weight Management and Nutrition Clinic, media advertising, classified ads, and existing databases of patients with obesity, including the phenome registry (Mayo Clinic IRB number [REDACTED]), the Mayo Clinic biobank and the right-10k cohort.

Inclusion criteria

- a) Adults with obesity ($BMI > 30 \text{ Kg/m}^2$); these will be otherwise healthy individuals with no unstable psychiatric disease and controlled comorbidities or other diseases.
- b) Age: 18-75 years.
- c) Gender: Men or women. Women of childbearing potential will have negative pregnancy tests within 48 hours of enrollment.
- d) Women of childbearing potential must agree to use a method of effective contraception during study participation.

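### Does the promise to show the importance of combining tracker and drug claim more than a drug-versus-placebo trial can deliver?

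*Combined protocol and SAP*

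**What the plan says.** The sentence at issue is the whole of the section Anticipated results and significance: "Our study will demonstrate the importance of combining a consumer-based wearable activity tracker with an Anti-obesity Pharmacotherapy in Obesity". The title has a similar slant, since it opens with the effect of the tracker.

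The rest of the document is consistent about what is compared:

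- **Evidence gap** (Introduction, end of Wearable Activity Trackers): "Little is known about the effect anti-obesity pharmacotherapy among patients undergoing lifestyle intervention that includes a consumer-based wearable activity tracker".
- **Hypothesis and Aims**: "anti-obesity pharmacotherapy (vs placebo) will have an effect on weight loss among patients using an activity tracker".
- **Tracker exposure** (Methods/Study Design): "All the participants will receive a wearable activity tracker and digital wellness devices". The Wearable tracker section makes use of the watch compulsory, and exclusion criterion h removes a "Participant unable or unwilling to follow protocol including use of the wearable activity tracker".
- **Randomised factor** (Methods/Study Design): "Subjects will be randomized 1:1 to placebo or Phentermine-topiramate ER". Randomization and Allocation agrees: "Randomization will be based on guiding pharmacotherapy or placebo".
- **Sample size and analysis** (Statistical Considerations; Statistical Analysis): differences of 1, 1.5 and 2 kg between active and placebo, tested by ANCOVA on 3-month weight adjusted for baseline weight.

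**The concern.** To show that combining two things matters, one would normally want a group that has only one of them. Here there is no group on drug without tracker and no group with neither. The tracker is a constant, so the trial cannot show that it adds anything.

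The plan itself treats the tracker's long-term value as unsettled. It says that "numerous wearable technologies specific to physical activity and diet are widely adopted with minimal long-term data or benefits", although the same section also cites a meta-analysis with significant gains in steps, moderate-to-vigorous activity and energy expenditure. The plan offers no evidence that trackers reduce weight. For the drug, the Introduction reports a loss of 10.2 kg against 1.4 kg on placebo over 56 weeks, at a higher dose than this trial uses and with no tracker mentioned.

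A drug-placebo difference could therefore appear here whether or not the tracker contributes. If a positive result were written up in the words of the significance section, a reader might credit the tracker with a share of it. What would be at stake is the interpretation of the trial. The validity of its test is not in question.

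**Working it through.** **Inputs.** From Methods/Study Design and Statistical Considerations: 80 participants, 1:1 allocation, tracker for all, SD 3 kg. From Statistical Analysis: final two-sided significance level 0.0492.

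**1. The plan's own figure.** The table does not state its alpha or power. I assume two-sided 0.05 and 80%. The normal approximation is

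n per group = 2 × (1.960 + 0.842)² × 3² / δ²

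which gives 142, 63 and 36 for δ = 1, 1.5 and 2 kg. The t-test version gives 143, 64 and 37, exactly the printed values. The sizing is therefore a drug-versus-placebo calculation with no tracker contrast in it.

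**2. What the design can estimate.** Planned numbers are 80 / 2 = 40 per arm, with 80 − 80 = 0 participants lacking a tracker. Write the full model as

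weight = b0 + b1·drug + b2·tracker + b3·drug·tracker.

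With tracker = 1 for everyone it collapses to

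weight = (b0 + b2) + (b1 + b3)·drug.

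The design matrix has rank 2 out of 4 columns. The estimable effect is b1 + b3, the effect of the drug in people who have a tracker. Neither b2 nor b3 can be separated out, and more participants would not help.

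**3. Set against the hypothesis.** The hypothesis asks for the effect of the drug among tracker users, which is b1 + b3. The estimable quantity and the stated aim are the same.

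**4. Set against the disputed sentence.** It has two readings.

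| Reading | What it needs | Available? |
|---|---|---|
| Adding the drug to tracker-based care is worthwhile | b1 + b3 | Yes, randomised |
| The tracker adds to the drug, or the two interact | b2 + b3, or b3 | No |

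The first reading matches the evidence gap stated just before the hypothesis. The second appears in no objective, endpoint or analysis.

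**5. What a rewording would change.** The drug contrast has standard error 3 × √(2/40) = 0.67 kg. Power for 2 kg at 0.0492 is 83.6% with 40 per arm and 74.5% with 32 per arm (20% dropout). All of these stay as they are under any wording of the significance section. Whether 80 is enough once dropout is allowed for is a separate question, not judged here.

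**6. Other places where a tracker claim might enter.** Steps and hours of tracker use are compared between arms, which shows what the drug does to tracker use and says nothing about what the tracker does to weight. The exploratory aim compares adherent with non-adherent patients and tests adherence by drug, with adherence set at 80% use in the first 3 months. Adherence is observed after randomisation among people who all have a tracker, so it does not identify a tracker effect either. The plan labels it exploratory.

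**The case for a change.** The best case for a change is that the disputed sentence is the plan's only statement of what its result will mean, and it makes the combination the thing to be shown. The title leans the same way. The verb also presumes a positive result. Because the tracker's benefit is an open question by the plan's own account, the permitted conclusion should be fixed before the data are seen, and the cost is a sentence or two.

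The factual part of this stands: no tracker effect is identifiable, and the wording admits a reading that the design cannot support. The need for a change does not follow. The permitted conclusion is already fixed where it counts, in the hypothesis, the design statement, the sample-size table and the primary ANCOVA, all of which name drug versus placebo. The harm rests on a reader passing over those sections in favour of one aspirational line.

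A blanket disclaimer about the tracker would also have its own cost. It would bear on how the exploratory adherence aim may be reported, and the plan leaves it unclear whether use there means tracker use or exercise adherence. At most a bar on causal claims would be defensible, and the non-randomised nature of that comparison already implies one.

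**Conclusion.** The concern does not call for a change. The observation behind it is correct: all 80 planned participants have a tracker, so the trial informs on the drug in tracker users and on nothing about the tracker itself. But this is loose wording in a significance statement, with a valid reading available and the right comparison specified in every operative section. Rewording would alter no procedure, endpoint, sample size, model, significance level or result. The title's phrasing is the same kind of editorial matter, since its combination wording can be taken as describing the setting.

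This rests on two assumptions: that trackers are supplied to everyone as planned, and that the results are reported against the stated hypothesis. The identifiability argument does not depend on the SD, the dropout rate or the sample size.
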